Rationale: Urothelial carcinoma of the bladder has a high recurrence rate, partly due to missed lesions at diagnostics with White Light Imaging (WLI) cystoscopy. Storz Professional Image Enhancement System (SPIES) is a new technique that visually enhances the images in order to improve diagnostic accuracy. SPIES assisted TURBs are expected to result in lower recurrence rates of bladder tumor compared with White Light TURBs.

Objective: To compare the recurrence rate of tumor at 12 months following SPIES assisted TURB with WLI assisted TURB in patients with non-muscle invasive bladder cancer (NMIBC Ta/T1/CIS).

Study design: This study is a multicenter randomized controlled trial in which the efficacy between SPIES assisted and WLI assisted TURB are compared. Subjects in the experimental arm (Arm A) will undergo SPIES assisted TURB, whereas subjects in the control arm (Arm B) will receive treatment with WLI assisted TURB only. Baseline characteristics will be recorded, as well as short and long-term follow up.

Study population: The study population comprises those patients who are presenting with primary or recurrent urothelial bladder cancer (NMIBC stage Ta, T1 or CIS) in the participating centers.

Intervention: All patients will undergo TURB. Patients in Arm A will undergo SPIES and WLI assisted TURB, and patients in Arm B will undergo WLI only assisted TURB.

Main study parameters/endpoints: Primary end point of the study is recurrence rate of tumor at 12 months after TURB in the two arms. Secondary end points include recurrence rates at 3 months and 3 years.

Nature and extent of the burden and risks associated with participation, benefit and group relatedness: The burden and risk associated with participating in this trial does not differ for patients in the experimental or the control arm. In both groups patients will undergo TURB, and will be followed for a maximum of three years at several site visits, in accordance with existing guidelines for follow up.

1. INTRODUCTION AND RATIONALE

Urothelial carcinoma (UC) develops in the bladder and the upper urinary tract (UUT). Non-muscle-invasive bladder cancer (NMIBC) includes stages Ta, T1 and carcinoma in situ (CIS) and it accounts for 75% of primary diagnosed bladder tumors. Recurrence rates of UC are exceptionally high, which calls for extensive diagnostics and surveillance strategies.

Percentages on recurrence from EORTC studies have been estimated to range from 15% to 61% at one year after surgery. Risk for recurrence is associated with stage, grade and number of tumors, while progression is associated with grade and the presence of CIS (Sylvester et al., 2006).

Diagnostics of UC of the bladder is usually performed by the visual approach including the need for biopsies or transurethral resection of the bladder (TURB). Most tumors can be identified by White Light (WL) cystoscopy. However, especially CIS is difficult to identify using this procedure. Non-identified tumors can later appear as recurrence, some of which becoming invasive. This demonstrates the need for a procedure that more accurately detects bladder tumors. Since a more accurate detection of tumors leads to more targeted treatment and better complete resection, the rate of recurrence may decrease with such procedures.

The use of photodynamic agents e.g. HEXVIX has been shown to be helpful in these cases in order to accomplish a better resection, identify “overlooked” tumors, and to target biopsies in case of a positive cytology only. This translates into more complete resection, reducing the recurrence rate of non-invasive tumors (Stenzl et al., 2010) and in more appropriate treatments (Mowatt et al., 2011). The technique of Narrow Band Imaging (NBI) is being studied at the moment. This technique uses a light filter, which results in enhancement of the fine structures of the mucosal surface (Cauberg et al., 2010). KARL STORZ has developed a new technique that is now ready for clinical evaluation. With Storz Professional Image Enhancement System (SPIES), no endoscopic filter is needed to enhance the image in order to gain more clarity. SPIES is based on a new software platform, which uses the different light wavelengths to produce images with different contrast specifications. SPIES offers a technique which could be useful in bladder cancer treatment, since clearer images are likely to result in reducing the numbers of tumors that are missed by the gold standard White Light Imaging (WLI). Additionally, once the tumor is detected, SPIES images may help find the demarcation between tumor and healthy tissue, resulting in more complete resection of the tumor(s). The Clinical Research Office of the Endourological Society (CROES) has initiated this study, because patients could benefit from better imaging during TURB. The recurrence

rate is expected to be decreased with the use of SPIES by obtaining a more complete resection, meaning the patient will need less invasive diagnostic and surgical visits.

2. OBJECTIVES

Primary Objective:

1. To compare the recurrence rate of tumor at 12 months following SPIES assisted TURB (Arm A) with White Light Imaging only assisted TURB (Arm B) in patients with primary or recurrent non-muscle-invasive urothelial bladder cancer (NMIBC Ta/T1/CIS). A subgroup analysis will be carried out for patients presenting with only primary tumors.

Secondary Objectives:

1. To assess the recurrence rate of tumor at short and long term follow up (3 months and 3 years) after SPIES or WLI assisted TURB in patients with NMIBC.
2. To assess the peri-operative morbidity (30 days) between SPIES and WLI assisted TURB by comparing the proportion of adverse events and using the Clavien-Dindo score.

2.1 Study design

This study is a multicenter randomized controlled trial in which the recurrence rates of cancer between SPIES assisted and WLI assisted TURB are compared. Randomization is stratified by tumor multiplicity (single or multiple), tumor status (primary or recurrent) and macroscopic findings (papillary or flat, where CIS is scored as flat lesion). Patients randomized into the experimental arm (Arm A) will undergo SPIES and WLI assisted TURB, whereas the patients in the control arm (Arm B) will undergo WLI only assisted TURB. WLI is chosen as control, since it is considered the gold standard for detecting bladder tumors. Short and long term follow up will be recorded in order to evaluate the health gains for patients over a longer period. Perioperative (30 days) complications will be compared between the two treatment arms to evaluate the safety of SPIES.

Each participating center must submit this protocol to their local MEC and each participating center is responsible for the insurance of their patients. Data from all participating centers will be collected through electronic Case Report Forms (eCRFs), with use of an online Data Management System (DMS), which is located and maintained at the CROES office.

Members of the CROES office will perform all analyses. Each center willing to participate should have enough experience and be familiar with SPIES. A center is considered to have enough experience when a minimum of 10-20 procedures have already been done with SPIES prior to including patients in this study.

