3.3 Randomisation and treatment allocation

Patients presenting with a bladder cancer and who are scheduled for TURB or patients who are scheduled for random biopsies and/or TURB because of a bladder wash out or voided urine with malignant (G3) cells will be included in the study. Eligible patients who are willing to participate will be randomized in a ratio of 1:1 to either Arm A (SPIES+WLI assisted TURB) or Arm B (WLI assisted TURB). The CROES will utilize the randomization to minimize systematic error and potential selection bias by the investigators. The randomization will be performed by using randomly permuted blocks (computer generated), with block size of 6. To assure balanced characteristics and comparable prognosis between the two arms, the

randomization will be stratified on tumor multiplicity (single or multiple), tumor status (primary or recurrence) and macroscopic findings at time of baseline visit (papillary or solid/flat tumor [including CIS]), leading to 8 stratification groups.

Concealment of treatment allocation is achieved by: 1) reducing the time between randomization and intervention, 2) first deciding whether the patient meets all study entry criteria, and 3) if so, randomize the patient in the DMS. The randomization will take place just before the intervention starts; ideally both occur on the same day. The DMS performs the randomization then reveals treatment allocation. The patients will be blinded to their allocation. Due to the nature of the procedure, the surgeon will not be blinded.

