3.5 Surgery procedures

At Visit 2, as described in the preceding paragraphs, patients will undergo TURB. The procedure for TURB is described in this paragraph, for patients in both treatment Arm A and Arm B.

The following procedure will be utilized to accomplish the cystoscopic examination of each patient:

For patients allocated to treatment Arm A (SPIES):

1. Turn on the white light. Inspection of the bladder and indicating all papillary lesions and flat and suspicious lesions seen on a bladder diagram.

2. Turn to the SPIES software image. Inspection of the bladder and indicating all papillary lesions and flat and suspicious lesions seen on a bladder diagram (Appendix A). The choice of SPIES-platform (i.e. Clara, Chroma, Spectra A or Spectra B) is to the discretion of the investigator, and will be recorded. The use of the SPIES-VIEW mode, which provides two images at the same time (WL and SPIES) on the same screen, is allowed and is to the discretion of the investigator.
3. Perform complete resection (TURB) of all papillary lesions, and obtain biopsies of all flat lesions and suspicious areas. Choice of modality (SPIES or WL) for resection is to the discretion of the investigator, and will be recorded.

For patients allocated to treatment Arm B (WLI):

1. Turn on the white light. Inspection of the bladder and indicating all papillary lesions and flat and suspicious lesion seen on a bladder diagram (Appendix A).
2. Perform complete resection (TURB) of all papillary lesions, and obtain biopsies of all flat lesions and suspicious areas.
3. The patient will be treated to normal hospital routines

All positive or suspect areas will be resected or biopsied using WL or SPIES. All papillary lesions must be resected completely.

Adjuvant treatment is up to the local investigator, however we recommend standardization for low-, intermediate, and high-risk groups (as defined by EORTC).

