5.3 Other study parameters

Multivariate analyses will be performed to assess possible associations with surgeon experience, geographical differences and risk factors for complications after surgery.

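### The SPIES experience rule in section 2.1 is a range counted per centre, and section 3.3 does not fix the surgeon before allocation is revealed, so operator experience and operator mix in the arms are uncontrolled

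*Protocol*

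**What the plan says.** Section 2.1 makes SPIES experience a condition of taking part: "Each center willing to participate should have enough experience and be familiar with SPIES". It then defines the condition: "A center is considered to have enough experience when a minimum of 10-20 procedures have already been done with SPIES". Both sentences are about the centre. The protocol sets no number of SPIES procedures for the individual surgeon.

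Section 3.5 describes what the operator does in Arm A: inspect under white light, inspect again under SPIES with a platform of the operator's choosing, then resect and biopsy. On the last step it says: "Choice of modality (SPIES or WL) for resection is to the discretion of the investigator, and will be recorded".

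Section 3.3 covers allocation. On timing: "The randomization will take place just before the intervention starts; ideally both occur on the same day". On disclosure: "The DMS performs the randomization then reveals treatment allocation". On blinding: "Due to the nature of the procedure, the surgeon will not be blinded". On balance: "randomization will be stratified on tumor multiplicity (single or multiple), tumor status (primary or recurrence) and macroscopic findings at time of baseline visit". Neither surgeon nor centre is a stratification factor, and nothing says when the operator is chosen.

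Section 5.1 compares two proportions at one year. Surgeon experience appears only in section 5.3, under other parameters: "Multivariate analyses will be performed to assess possible associations with surgeon experience".

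**The concern.** By setting an experience condition, the sponsor accepts that SPIES needs some practice before trial patients are treated. The condition as written does not secure that practice. A centre can qualify on one surgeon's cases while a colleague with none operates in Arm A. A centre with 12 procedures passes if the minimum is 10 and fails if it is 20.

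Two separate consequences follow.

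- **Dilution.** If some Arm A cases are done by surgeons still learning SPIES, the average benefit in Arm A shrinks. A null result could then not be told apart from an incomplete run-in.
- **Different operators by arm.** Once the arm is known and the operator is still open, a centre whose SPIES experience sits with one or two people can send Arm A to them and Arm B to others. Randomising patients does not balance a choice made after allocation. The bias goes whichever way the surgeons differ in skill.

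**Working it through.** **Inputs from the protocol.** Section 2.5: 35% control recurrence at one year, 10-point difference, two-sided 5%, 80% power, continuity-corrected test, 349 per arm in the primary-tumour subgroup, about half of all patients with primary tumours, 1,928 in total. Section 3.4.9: 15 centres. Section 2.1: 10-20 procedures per centre.

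**Assumptions not in the protocol.** Number of surgeons per centre, k. Share of the benefit that a learning surgeon's patients still receive, g. Surgeons gain SPIES experience only from Arm A cases. The control rate is 35% in recurrent tumours too.

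**1. The protocol's own figure.** Without correction, n = [1.96√(2×0.30×0.70) + 0.842√(0.35×0.65 + 0.25×0.75)]² / 0.10² = 328.5, so 329. With correction, (329/4)×[1 + √(1 + 4/(329×0.10))]² = 348.7, so 349. This matches. The inflation chain also follows: 349×1.15 = 401, 401.35×1.20 = 482, 482×2×2 = 1,928.

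**2. Arm A cases per centre.** 964/15 = 64.3.

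**3. Share of Arm A done during learning.** If every surgeon must reach m cases and the centre starts with m in total, the learning cases number mk − m = m(k−1). This does not depend on how the first m were shared. The share is f = m(k−1)/64.3.

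- m=10, k=3: 20/64.3 = 31%
- m=10, k=5: 40/64.3 = 62%
- m=20, k=3: 40/64.3 = 62%

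The last line shows that the choice within the 10-20 range matters.

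**4. Diluted difference.** d = 10×[1 − (1−g)f] points. With g = 0.5, d is 8.4 points at f = 31% and 6.9 points at f = 62%.

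**5. Power.** Φ{[d − 1/n − 1.96√(2p̄(1−p̄)/n)] / √([pA(1−pA) + pB(1−pB)]/n)}, with pB = 0.35, pA = 0.35 − d and p̄ their mean.

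At n = 349:
- d = 0.100: (0.1000 − 0.0029 − 0.0680)/0.0345 = 0.84, power 80%
- d = 0.0844: (0.0844 − 0.0029 − 0.0685)/0.0348 = 0.37, power 65%
- d = 0.0689: (0.0689 − 0.0029 − 0.0690)/0.0351 = −0.08, power 47%

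The full population has about 2×349 = 698 evaluable per arm. The same formula gives 98%, 92% and 77%.

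Range over g:

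| Share learning (f) | Benefit kept (g) | d (points) | Power, 349 per arm | Power, 698 per arm |
|---|---|---|---|---|
| 0 | – | 10.0 | 80% | 98% |
| 31% | 0.75 | 9.2 | 73% | 96% |
| 31% | 0.5 | 8.4 | 65% | 92% |
| 31% | 0 | 6.9 | 47% | 77% |
| 62% | 0.75 | 8.4 | 65% | 92% |
| 62% | 0.5 | 6.9 | 47% | 77% |
| 62% | 0 | 3.8 | 16% | 30% |

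**6. Different operators by arm, no SPIES effect.** Suppose SPIES-trained surgeons do 75% of Arm A and 25% of Arm B (assumed). The spurious difference is their skill advantage × (0.75 − 0.25). An advantage of 5 points gives 2.5 points, and one of 10 points gives 5. Two-sided rejection, without continuity correction, rises from 5% to 11% and 29% at 349 per arm, and to 17% and 51% at 698. A larger sample does not remove this error. With the same surgeon mix in both arms the rate stays at 5%.

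**The case against.** The strongest case against giving this much weight has five parts.

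- **Power of the primary comparison.** A reader might infer from 65% and 47% that the primary objective is underpowered. The documents do not support that. Section 2.5 ties 349 per arm to the primary-tumour subgroup, whereas the primary objective in section 2 covers primary and recurrent tumours together. There the same assumptions leave 92% and 77%. This objection stands, and the two sets of figures must be kept apart.
- **Direction.** A reader might infer that a learning curve would be measured as a SPIES benefit. It would not: learning in Arm A alone pulls the result towards no difference. A spurious benefit needs different surgeons in the two arms.
- **Assignment by arm.** A reader might infer that the protocol gives the arms to different surgeons. It does not prescribe this. It only fails to prevent it, and randomising just before surgery, ideally on the same day, leaves little time to swap operators. That lowers the likelihood but does not exclude it.
- **Safeguards.** Every Arm A case begins with a full white-light inspection, platform and modality are recorded (section 3.5), and centres are academic (section 2.2) and need council approval (section 7.3). These limit the harm, but none concerns the operator's SPIES experience or who operates in which arm.
- **Later analysis.** An SAP, not available here, could add a surgeon term to a sensitivity analysis. If surgeon and arm largely coincide, such a term cannot reliably separate skill from SPIES. The section 5.3 analysis has no stated experience measure and is not tied to the section 5.1 comparison.

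Qualifying centres rather than surgeons can be a deliberate choice where the question is how SPIES performs in participating centres. Even then, the range has to become one number.

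**Conclusion.** The concern holds in a limited form. The section 2.1 rule is not one usable threshold and does not ensure that an Arm A operator has used SPIES before. Section 3.3 leaves the operator open when the arm becomes known. The two gaps act differently: the first dilutes, the second can bias either way.

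The protocol does not give what is needed to size either one. Surgeons per centre, the learning effect and the skill differences are all assumed. With k from 3 to 5, m = 10 and a halved effect, the loss is material for the subgroup that drove the sample size and modest for the full population. Only the more severe case (k = 5) takes the full population slightly below the planned 80%. The false-positive figures show what would happen under one assumed imbalance and are not a forecast. This is a worthwhile, inexpensive improvement to the design and does not show that the primary comparison fails.

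**What to change.** - **Section 2.1.** Replace the range with one number, chosen by the sponsor from its own 10-20, and apply it to each surgeon who operates on trial patients.
- **Section 3.3.** Require the operating surgeon to be entered in the data management system before allocation is revealed, with that surgeon performing the TURB whichever arm is drawn.

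The cost is a wording change, a per-surgeon log at site approval and one extra field in the data management system. A few surgeons may start later or not operate in the trial, which could slow recruitment slightly at some centres.

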2.2 Population

The study population comprises those adults (aged 18 years or above) who are presenting with primary or recurrent urothelial bladder cancer in the participating centers (NMIBC: Ta/T1/CIS). Patients are supposed to have been diagnosed with NMIBC after WL exploration a maximum of 30 days before inclusion in the study. Participating centers are those that have been selected to take part in this study. All are academic centers where primary health care is provided.

2.3 Inclusion criteria

In order to be eligible to participate in this study, a subject must meet all of the following criteria:

- Has signed informed consent
- Is scheduled for treatment of a primary or recurrent NMIBC
- Is aged 18 years or older
- Has or has had no tumors in the upper urinary tract
- Has had no previous irradiation of the pelvis

2.4 Exclusion criteria

A potential subject who meets any of the following criteria will be excluded from participation in this study:

- Gross haematuria at the time of TURB (i.e. heavy bladder bleeding resulting in marked amounts of blood in the urine which may interfere with cystoscopy)
- Participation in other clinical studies with investigational drugs either concurrently or within the last 30 days
- Pregnancy or breast-feeding (all women of child-bearing potential must document a negative serum or urine pregnancy test at screening and are suggested to use the contraceptive pill or an intrauterine device (IUD) during the treatments and for at least one months thereafter)
- Conditions associated with a risk of poor protocol compliance
- Has had instillation therapy in the six months prior to the screening visit

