5.4 Handling missing and spurious data

When missing data occurs in the primary outcome variable, a sensitivity analysis will be performed. In the sensitivity analysis, the missing data at three months will be substituted by the value "recurrence", unless the result at later follow up is "no recurrence". Missing data at twelve months will be substituted by the value "recurrence", unless the result at later follow up is "no recurrence". Missing data at three years will be substituted by the value "recurrence". In the analyses of secondary objectives, analyses will be carried out on available data, with reporting of proportions of missing data.

All analyses will be performed using software SPSS 20, Stata 13 and R 3.0 or higher. Analysis will be based on the principle of intention-to-treat. All patients who signed the

informed consent form, met the study entry criteria and underwent randomization will be included in the analysis.

Results will be presented in tables reporting at least the number of subjects, mean, standard deviation, minimum and maximum for continuous data; and number of subjects and percentages for categorical data.

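### The gross haematuria exclusion is dated to the TURB, after the arm is revealed, and sections 5.1 and 5.4 disagree on whether a patient found ineligible then stays in the analysis

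*Protocol*

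**What the plan says.** Section 2.4 lists as an exclusion "Gross haematuria at the time of TURB (i.e. heavy bladder bleeding resulting in marked amounts of blood in the urine which may interfere with cystoscopy".

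Section 3.3 sets the order of events. Its concealment steps include "first deciding whether the patient meets all study entry criteria, and 3) if so, randomize the patient in the DMS". On timing it says: "The randomization will take place just before the intervention starts; ideally both occur on the same day". It continues: "The DMS performs the randomization then reveals treatment allocation". It also states: "Due to the nature of the procedure, the surgeon will not be blinded".

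Section 3.4 places the eligibility evaluation at Visit 1, and surgery at Visit 2 may follow up to 14 days later. The Visit 2 list includes an assessment of bladder symptoms before TURB, but nothing says that this comes before randomisation.

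The analysis set is described twice, each time as intention-to-treat. Section 5.1 includes every randomised subject. Section 5.4 adds a condition: it covers patients who signed the "informed consent form, met the study entry criteria and underwent randomization will be included in the analysis".

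**The concern.** Sections 2.4 and 3.3 do not fit together. One ties a criterion to the moment of surgery. The other wants every criterion closed before a randomisation that comes before surgery, possibly on an earlier day. When bleeding first becomes apparent between the release of the allocation and the operation, a literal reader of 2.4 can still declare the patient ineligible. The person making that judgement may be a surgeon who knows the arm.

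Section 5.4 then determines the consequence. A patient who fails an entry criterion is outside its analysis set, so a decision made with the arm known could remove a randomised patient. If such removals differ between arms and the patients removed differ in prognosis, the 12-month recurrence comparison is biased. Section 5.1 would prevent this, but neither section is given precedence.

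**Working it through.** **Setting the sections side by side**

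| Question | Section | Answer |
|---|---|---|
| When is the haematuria criterion fixed? | 2.4 | At the time of TURB |
| When must all criteria be settled? | 3.3 | Before randomisation |
| When is randomisation? | 3.3 | Just before TURB, same day ideal but not required |
| Who knows the arm at TURB? | 3.3 | The surgeon |
| Is a randomised patient who fails a criterion analysed? | 5.1 | Yes |
| Same question | 5.4 | No |

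If the check and the randomisation both take place on the day of surgery, in that order, 2.4 and 3.3 can both be met. If TURB falls on a later day, they cannot, because the state at TURB is not yet known when the patient is randomised.

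**The plan's own figures, used as inputs**

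Section 2.5 gives 349 per arm for 35% against 25%, two-sided 5%, 80% power, with continuity correction. This reproduces exactly. The inflation also reproduces: 349 × 1.15 = 401.35; × 1.20 = 481.6, rounded to 482; 482 × 2 arms × 2 = 1,928, or 964 per arm. The present point changes none of these figures.

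**Size of a possible bias (assumed values)**

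The protocol gives no rate of gross haematuria at TURB and no rate of exclusion after randomisation. Assumptions:
- There is no true effect, so both arms have p = 35% recurrence at one year (the control rate in 2.5).
- A share x of one arm only is removed, with x from 1% to 5% (assumed).
- Those removed have recurrence risk r. The values are 35% (average), 50% (assumed) and 61% (the top of the one-year range quoted in section 1).

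Rate among those left: p' = (p − x·r)/(1 − x). Shift = p' − p = −x(r − p)/(1 − x).

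| x | r = 35% | r = 50% | r = 61% |
|---|---|---|---|
| 1% | 0 | −0.15 points | −0.26 points |
| 2% | 0 | −0.31 | −0.53 |
| 3% | 0 | −0.46 | −0.80 |
| 5% | 0 | −0.79 | −1.37 |

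Example: x = 5%, r = 61% gives (0.35 − 0.0305)/0.95 = 33.63%, a shift of −1.37 points.

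The two-sided error rate is Φ(−1.96 − d) + Φ(−1.96 + d), where d = shift/SE and SE = √[p'(1 − p')/(N(1 − x)) + p(1 − p)/N]. For the same example with N = 964, SE = 0.0219, d = −0.62, and the error rate is 9.6%. Over the r = 50% and r = 61% columns it runs from 5.1% to 9.6% with 964 per arm, and from 5.0% to 6.6% with 349 per arm. The sign of the bias depends on which arm loses patients.

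**The case against.** The strongest reply is that the protocol already states the right order. Section 2.4 addresses potential subjects, and 3.3 puts eligibility first. The defining sign in 2.4 is marked blood in the urine, and interference with cystoscopy is only a possible consequence. A check just before a same-day randomisation therefore complies with both sections. No section provides for removing a randomised patient because of haematuria; section 3.6 names only the subject's own wish and urgent medical reasons. Section 5.1 keeps everyone randomised.

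Most of this stands, and it rules out reading judgement after the reveal as the protocol's intended procedure. Two gaps remain. Same-day randomisation is not required, and no haematuria check is tied to the release of the allocation. Nor can 5.1 be relied on while 5.4 says something narrower under the same label.

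A reader might also infer three stronger things, none of which the documents support:
- **That a bleeding bladder would be called unworkable more readily in Arm A**, because section 2.8 says SPIES suppresses red and draws on contrast related to haemoglobin. Nothing says that SPIES performs worse in blood. Section 3.5 starts both arms with a white-light inspection, and 2.8 lets the surgeon switch between modes.
- **That haematuria can be seen only once the scope is in.** The definition in 2.4 does not say so.
- **That concealment is defeated.** Concealment protects the decision to enrol before the arm is known. A later exclusion is a problem of who is analysed.

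The numerical case against is also fair. The largest figures need wholly one-sided removal: 5% of 964 is about 48 patients from one arm and none from the other, all at raised risk. Nothing in the protocol links haematuria to recurrence.

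**Conclusion.** The point holds as a conflict in the text that leaves room for bias; it is not a demonstrated bias. The timing in 2.4 does not fit the order in 3.3, and 5.1 and 5.4 give opposite answers for a randomised patient later judged ineligible. Followed literally, 2.4 together with 5.4 allows a patient to be dropped with the arm known.

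The direction is unknown and the size probably small. One-sided removal of 1% to 5% at above-average risk moves the difference by about 0.15 to 1.4 points, against the 10-point difference in section 2.5. The shift is zero if those removed have average risk or if the arms lose the same share of patients at the same risk. The removal rates, their one-sidedness and the raised risk are all assumptions. The correction is worth making because it is specific and nearly free, not because a large distortion is expected.

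**What to change.** 1. Reconcile 2.4 with 3.3. Word the criterion so that it is assessed on the day of TURB and before randomisation, and make the answer a mandatory field that the data management system requires before it releases the allocation.
2. Reconcile 5.4 with 5.1. State one intention-to-treat set in which every randomised patient is analysed in the allocated arm, whatever bleeding is found later. Bleeding first noted after randomisation is recorded but does not remove the patient from the analysis. Clinical handling of such patients is left to the investigator.

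The cost is two wording changes and one data field. The downside is that a few patients with a poor view at surgery stay in the analysis and slightly dilute any effect. Tying the check to the day of TURB also means that randomisation must take place that day, which 3.3 already calls ideal.
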